# 8.1.2 Multiple Ascending Dose (MAD) part of the trial

In Part B, repeated, oral doses of C106 will be administered in 4 sequential dose cohorts. Within each cohort, subjects will be randomised to receive C106 (n=6) or placebo (n=2). The initial dose, dose escalations, and dosing schedule will be based on emerging safety, tolerability, and PK data observed in the SAD part of the trial (Part A) and on emerging data from the MAD part. Each dose level during the Part B will be selected such that the predicted maximum exposure will not exceed the maximum exposure (based on AUC and  $C_{max}$ ) in previously evaluated SAD cohorts. The proposed doses are 40, 100, 180 and 240 mg BID. Twice daily dosing for 8 days is planned. Based on emerging PK data, once daily (QD) dosing may be applied if recommended by the iSRC. The number of dosing days may also be changed based on PK data from Part A (SAD), with the aim to reach steady state during the dosing period. The treatment duration will, however, not exceed the treatment duration in preclinical toxicology studies *i.e.*, 28 days. One additional dose cohort can be explored based on emerging safety, tolerability, and PK of the drug, if recommended by the iSRC. The maximum oral daily dose in Part B will not exceed 480 mg C106.

Subjects will come for 3 visits to the CRU. Screening (Visit 1) will take place within 4 weeks of the first dose (Day -28 to Day -1) and will include the subject's signing of the informed consent and an eligibility check, see Table 8.1-3 for details. At Visit 2, subjects will reside at the CRU from Day -1 (the day before IMP administration) until Day 10 for 8 days multiple dose IMP administration, safety, tolerability and PK assessments, see Table 8.1-3, Table 8.1-4 (Day -1 to Day ) and Table 8.1-5 (Day 8 to Day 10). Subjects must fast from 2 hours prior to each IMP administration until 1 hour after. During fasting, water, but no other drinks, is allowed as desired. No drinks are allowed for 1 hour before and 1 hour after dosing. On Day 8, only the morning dose will be administered (*i.e.*, in total 15 doses are planned).

The first 2 subjects in each cohort will be dosed in a sentinel fashion, 1 subject will receive C106 and the other will receive placebo as randomised. The subjects will be carefully monitored by clinical staff during and after dosing. Vital signs and ECG will be checked at regular intervals. There is immediate access to equipment, qualified staff and an ICU in case of an acute emergency. To give sufficient time for observation of any reactions there will be at least 24 hours before dosing of the remaining 6 subjects, who will be dosed in groups of 3 subjects at least 24 hours apart. A final end-of-trial visit (Visit 3) will take place on Day 22 ( $\pm 2$  days) or after early withdrawal.

For subjects participating in cohort B4, an assessment of endothelial function using EndoPAT will be performed before the first IMP administration (on Day -1 or 1), and  $30\pm10$  minutes after IMP administration on Day 7 (morning or evening). The EndoPAT assessments should be done at approximately the same time of the day on both occasions. Subjects must fast for at least 4 hours prior to the EndoPAT assessment until end of assessment. During fasting, water, but no other drinks, is allowed as desired. No drinks are allowed for 1 hour before and 1 hour after dosing.

Besides the starting dose and subsequent doses, also time points for safety and PK sampling may be adjusted as recommended by the iSRC following evaluation of emerging safety, tolerability, and PK data. If needed, one visit for additional safety and PK assessments may be added based on recommendations from the iSRC.

After collection of the last available 10 days data (48 hours after the last dose), there will be at least 2 weeks between dose escalations. Before initiating a new dose cohort, all subjects in the

previous cohort must have been treated and all available safety, tolerability and plasma concentration data up until and including 48 hours post last dose must have been evaluated by the iSRC. In case of non-replaced dosed dropouts, available data for the dropouts will be included in the iSRC evaluation. In case of dropouts, the iSRC may recommend including replacers to be able to make an informed recommendation on the next dose level. Based on emerging safety and PK data, the amount of required safety and PK data to be reviewed after a completed cohort might be adjusted.

Subjects are expected to participate in Part B for up to 47 days including a 28-day screening period.

The schedule of events for Part B is shown in Table 8.1-3 and is detailed for Visit 2 in Table 8.1-4 (Day -1 to Day 7) and Table 8.1-5 (Day 8 to Day 10).

Trial assessments are described in Section 11.

	Screening	Trial	intervent	ion and ob	oservati	on perio	d	Follow- up/End-of- trial	
Visit	Visit 1			Visit 2 	2			Visit 3	
Assessment/time- point	Day -28 to Day -1	Admission Day -1	Day 1	Days 2- 7	Day 8	Day 9	Day 10	Day 22 (±2 days) 	
Informed Consent	X								
Inclusion/exclusion criteria	X		Х						
Demographics	X								
Medical/surgical history	X								
HIV, hepatitis B and C	X								
Alcohol test	X	Х							
Weight/height (BMI)	X								
Serum FSH 	X								
Urine Drug Screen 	X	Х							
Physical Examination	X		X 					Х	
Clinical Laboratory Profile 	X	Х		Х	Х		Х	Х	
Safety urine sampling	X	Х		Х	Х		Х	Х	
Urinalysis (dipstick)	X	Х			X			Х	
Vital Signs 	X	Х	X	X	X	Х	Х	Х	
12-lead ECG	X		Х	Х	Х	Х	Х	Х	
Randomisation			Х						
IMP administration			Х	Х	Х				
Blood sampling for PK and metabolite profiling 			Х	X	Х	X	Х		
Urine sampling for PK and metabolite profiling 			X		X				
PD (EndoPAT) assessment 			Х	Х					
Meals 		Х	X	Х	X	X	Х		
Adverse events		X							
Prior and concomitant medications				X	[				

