A Phase 1 clinical trial with C21 reported reversible hair loss in 6 healthy subjects exposed to 200 mg C21 twice daily for 8 days (400 mg per day) (C21-003). The events included hair loss on the head and the body and occurred on average 11 (ranging from 8 to 14) days after end of dosing. Regrowth of the hair was observed in all subjects within 8 weeks after end of dosing. The observed hair loss was considered related to treatment with C21 and was possibly due to a pharmacological effect of stimulation of the AT2R. No cases of hair loss have been reported at dose levels up to 100 mg C21 twice daily for 7 days or after single doses of 200 mg in any of the completed, randomised, controlled clinical trials with C21.

As described in the current version of the IB (cut-off date 15-Mar-2022), mild to moderate "hair fall or hair loss" has been reported in 5 subjects in the ongoing, open-label IPF phase 2 trial after administration of 100 mg C21 twice daily (VP-C21-005). 4 out of the 5 cases have resolved; 3 out of 5 subjects continued treatment with C21. The characteristics and nature of the 'hair fall or hair loss' reported in this trial appear to be different from the hair loss reported in the phase 1 trial, and the relationship to treatment is unclear.

Although the mechanism for the reversible hair loss is not known, it cannot be excluded that it is a potential class effect related to high dose AT2R stimulation. It is therefore a risk that the subjects who participate in Part B of the current trial may experience hair loss. Hair loss of moderate intensity (*i.e.*, Common Terminology Criteria for Adverse Events [CTCAE] grade 2) in 2 subjects assessed as related to the IMP administration has hence been included as a stopping criterion for dose escalation, see Section 8.3.5.

The phototoxicity of C106 has not been investigated but based on the molar extinction coefficient (MEC) value obtained from absorbance studies a phototoxic potential cannot be excluded. Thus, sun protection, as defined in Section 9.6.1, should be used during the study.

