## Table 8.1-3 Schedule of events, Part B (MAD) Part B (MAD)

BMI=Body mass index. CTP=Clinical trial protocol. ECG=Electrocardiogram. FSH=Follicle stimulating hormone.

1. Details in separate flow charts (Table 8.1-4 and Table 8.1-5).

2. The duration of the intervention and observation period in Part B may be adjusted (8 days BID dosing duration

assumed). 3. Or after early withdrawal.

- 4. Females only (questionable cases).
- 5. Drug tests may also be performed at 1 to 2 additional random occasions during the trial.
- 6. Symptom driven physical examination
- 7. Clinical chemistry, haematology and coagulation, see Section 11.3.5.
- Systolic and diastolic blood pressure, pulse, respiratory rate at all visits indicated. Temperature will be measured on Day -1 only (other visits if indicated). For details regarding vital signs, see Section 11.3.4.
- 9. Metabolite profiling in plasma and urine at steady state only (Day 8 to Day 10).
- 10. Cohort B4 only. The EndoPAT assessment will be performed before the first IMP administration (Day -1 or Day 1) and 30±10 minutes after IMP administration on Day 7 (morning or evening dose). Subjects must fast for at least 4 hours prior to the EndoPAT assessment until end of assessment.
- 11. Breakfast at least 1-hour post-dose. Day -1 to Day 1 and Day 7 to Day 8: Standardised breakfast, lunch, snack, dinner and optional evening snack as applicable. Non-standardised meals Day 2, 3, 4, 5, 6, 9 and 10. For timing of meals, refer to Table 8.1-4 and Table 8.1-5.

# Table 8.1-4 Detailed schedule of events, Part B (MAD) Day -1 to Day 7

Day	Day -1							Day 1							Da	y 2	Da	Day 3 Days 4 to 7		
Assessment/time- point (hh:mm)	Ad- mission	Pre- dose	00:00	00:20	00:40	01:00	01:30	02:00	03:00	04:00	06:00	08:00	10:00	12:00	24 h	36 h	48 h	60 h	D4: 72 h D5: 96h D6:120 h D7:144h	D4:84h D5: 108h D6:132 h D7: 156 h
Inclusion/ exclusion criteria	Х	х																		
Urine drug screen	X																			
Alcohol test	Х																			
Physical examination		X1																		
Clinical laboratory. Profile	Х																X 		X 	
Safety urine sampling	Х																X 		X 	
Urinalysis (dipstick)	Х																			
Vital signs 	x	X			Х			Х		X	X		Х		X5		X5		X5	
12-lead ECG		X			X			X		X	X		X		X5		X5		X 	
Randomisation		X																		
IMP administration			X											Х	X	X	X	Х	Х	Х

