# 9.8.4 *Procedures for discontinuation of a subject from the trial*

A subject who prematurely discontinues participation in the trial will always be asked about the reason(s) for discontinuation and the presence of any AEs. If a subject withdraws consent, the Investigator must ask the subject if he/she is willing, as soon as possible, to be assessed according to the procedures scheduled for the end-of-trial visit in each part. Any ongoing AEs will be followed as described in Section 11.3.1.15.

The primary reason for discontinuation/early withdrawal must be specified in the eCRF and final drug accountability must be performed. If the primary reason is an AE, the AE must be specified.

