# 11.3.1.6 Time period and frequency for collecting adverse events

All AEs (including SAEs) will be collected from the signing of informed consent until the end-of-trial visit of each part.

Any AE with start date on the day of IMP administration must be recorded with start time.

At the end-of-trial visit, information on new AEs or SAEs, if any, and stop dates for ongoing events must be recorded as applicable.

Investigators are not obligated to actively seek AEs or SAEs after conclusion of the trial participation. However, if the Investigator learns of any SAE, including a death, at any time after a participant has been discharged from the trial, and he/she considers the event to be reasonably related to the trial intervention or trial participation, the Investigator must promptly notify the Sponsor.

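### Part B sets no interval from last dose for the early-withdrawal visit that ends AE collection, so the 8–14 day hair-loss period can go unobserved in subjects who stop early

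*Combined protocol and SAP*

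**What the plan says.** - **Final visit.** The synopsis and Section 8.1.2 give the same rule for Part B: "A final end-of-trial visit (Visit 3) will take place on Day 22" (±2 days), or after early withdrawal. Footnote 3 of Table 8.1-3 repeats the alternative, "Or after early withdrawal". None of these places gives a number of days from withdrawal or from the last dose.
- **Last dose.** Section 8.1.2: "On Day 8, only the morning dose will be administered".
- **End of AE collection.** Section 11.3.1.6: "All AEs (including SAEs) will be collected from the signing of informed consent until the end-of-trial visit of each part". The same section puts no duty on investigators to look for events after that. Section 11.3.1.15 extends follow-up past participation only for related serious or severe events that are already ongoing.
- **Delayed harm.** Section 6.3 reports that hair loss with C21 "occurred on average 11 (ranging from 8 to 14) days after end of dosing". It cannot rule out an effect of the class and names hair loss as a risk for Part B. Table 8.3-4 makes related grade 2 hair loss in two active subjects of one cohort a stopping criterion.
- **Consent withdrawal.** Section 9.8.4: "If a subject withdraws consent, the Investigator must ask the subject if he/she is willing, as soon as possible, to be assessed" by the end-of-trial procedures.
- **Analysis.** Under Section 17.3.1 a dosed subject with any post-baseline data is in the full analysis set (FAS). Section 17.5.1 summarises AE incidence by cohort, and Section 17.1 rules out imputation.

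**The concern.** For completers, the final visit falls at about the time when the delayed effect would show. For a subject who leaves early, the same visit is tied to leaving the trial and not to exposure. If it is held promptly, the last AE enquiry comes before the period in which the protocol itself expects hair loss could begin. A later case would be neither collected nor followed under the text, yet the subject would count in the denominator as event-free.

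Two features add to this. Some withdrawals are safety-driven: significant AEs (Section 9.8.1) and QTc (Section 9.8.2). And Section 9.8.5 excludes from replacement those Part B subjects withdrawn for AEs at least possibly related to treatment, so their missing observation is not made up. What is at stake is the completeness of the primary safety endpoint, and of the information behind the hair-loss rule, in cohorts with only 6 active subjects.

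**Working it through.** **1. The plan's own duration figures.** Formula: 28 screening days + nominal final-visit day + upper window.

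- Part A (Day 7 ±2): 28 + 7 + 2 = 37. Stated: 37. It reproduces.
- Part B (Day 22 ±2): 28 + 22 + 2 = 52. Stated in the synopsis and Section 8.1.2: 47. It does not reproduce. Without the window the sum is 50, and at the early edge 28 + 20 = 48.
- A 47-day maximum would put the latest possible visit on Day 47 − 28 = 19, which is 19 − 8 = 11 days after the last dose. On that figure even completers would not be observed to day 14.

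**2. Completers.** Interval = visit day − last dose day (Day 8).

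| Visit 3 | Days after last dose |
|---|---|
| Day 20 | 12 |
| Day 22 | 14 |
| Day 24 | 16 |

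The nominal visit reaches the end of the 8–14 day range. Visits on Day 20 or 21 (12 or 13 days) fall slightly short of it.

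**3. Early withdrawals.** Let the last dose be on day *s* and the visit *g* days later. The text sets no lower limit on *g*. The hair-loss period runs from day *s* + 8 to day *s* + 14. Any *g* from 0 to 7 complies and ends AE collection before the period opens. A *g* of 14 or more complies equally and covers it.

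For comparison, the existing Day 22 ±2 slot lies 20 − *s* to 24 − *s* days after a last dose on day *s*. For *s* = 6 that is 14 to 18 days, and longer for smaller *s*. For *s* = 7 it is 13 to 17 days. The present calendar can therefore hold a visit that covers the period.

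**4. Does stopping treatment mean leaving the trial?**

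| Place | What happens to the subject |
|---|---|
| Section 9.8.2 (QTc) | Withdrawn from the trial |
| Table 8.3-4, final row (related SAEs in two cohorts) | Dosing stopped and subjects withdrawn |
| Section 9.8.3 (liver) | Treatment stopped; withdrawal not stated |
| Table 8.3-4, related SAE, severe AE and hair-loss rows | Dosing stopped; withdrawal not stated |

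Where dosing stops without stated withdrawal, no follow-up schedule is given, so a reader cannot tell which version of Visit 3 applies.

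**5. What incomplete observation could do to the hair-loss count (illustration only).** Assume each active subject independently has risk *p*, an assumed value. The chance of seeing at least two cases among *n* observed subjects is 1 − (1 − *p*)^n − *n p* (1 − *p*)^(n−1).

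| *p* | *n* = 6 | *n* = 5 | *n* = 4 |
|---|---|---|---|
| 0.3 | 0.58 | 0.47 | 0.35 |
| 0.5 | 0.89 | 0.81 | 0.69 |
| 0.8 | 0.998 | 0.993 | 0.973 |

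The table supposes that an early stopper would have carried the same risk as a subject given all 15 doses. That may not be so.

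**The case against.** A reader might infer that early stoppers are seen as soon as possible by rule, and so always miss the period. The documents do not say this. That phrase stands only in Section 9.8.4, as a request to subjects who withdraw consent. For withdrawal because of AEs, QTc or other reasons the timing is open, and a later visit is equally compliant.

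A reader might also infer that the plan has no way to stop dosing while keeping safety follow-up, so that a stopped cohort could be lost entirely. That goes too far as well. The liver rule and most rows of Table 8.3-4 stop dosing and say nothing of withdrawal, and Section 15.6 requires suitable follow-up if the trial is terminated.

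The protocol has other safeguards. Residence may be prolonged (Section 6.3). The safety review committee may add a visit (Section 8.3.6) and considers late hair loss (Sections 6.3 and 8.3.6). Escalations are at least two weeks apart, and subjects keep a right to follow-up (Section 9.8.1).

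Finally, the 8–14 day range comes from six subjects given C21 at 200 mg twice daily for a full 8 days. Section 6.3 reports no hair loss in the completed trials at up to 100 mg twice daily for 7 days.

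All of this stands, and it limits the point. It does not remove it: none of these provisions requires contact with an early stopper 8 to 14 days after the last dose, and the committee can consider only what has been reported to it.

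**Conclusion.** The point holds in this form: the text allows AE collection to close before the 8–14 day period for subjects withdrawn early, although it does not require that. It also leaves unclear whether stopping treatment means leaving the trial. This is more than missing detail, because a site that follows the protocol exactly can cut short the observation of a harm on which the protocol bases a stopping rule.

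The size cannot be stated. It depends on the number of early stoppers, the day they are seen and the hair-loss risk after shortened C106 dosing, and the documents give none of these. For the same reason it would be wrong to conclude that reported incidence is biased low by a known amount, or most at the highest doses; no withdrawal figures by dose support that. The conclusion assumes that the C21 timing is relevant to C106, as the protocol itself does in part. It also assumes that incidence is computed on the FAS without regard to length of follow-up, since Section 17 describes no such adjustment.

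The 47-day figure is a separate, definite inconsistency of 5 days against Day 22 ±2.

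**What to change.** Reconcile the Part B synopsis, Section 8.1.2, Table 8.1-3 footnote 3, Section 9.8.4 and Section 11.3.1.6 with Section 6.3, Table 8.3-4 and Section 8.3.6:

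- State that stopping treatment is separate from leaving the trial, and bring Sections 9.8.2 and 9.8.3 and the rows of Table 8.3-4 into line on what follow-up applies.
- For early stoppers who have not withdrawn consent, define the end of AE collection (the Visit 3 already planned) relative to their own last dose, so that it covers the delayed hair-loss period as it does for completers. The sponsor sets the exact interval.
- Correct either the 47-day participation or the visit day, so that the two agree.

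The cost is amendment wording and a defined time for a visit that is already planned, for what should be few subjects. The downside is that some early stoppers may not return for a later visit, so the assessments at discharge should be kept as well.

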Blood sampling for PK		x		x	x	X	x	x	X	x	X	x	x	X 	X6		X6		X 	
Urine sampling for PK 		X						2	K 											
PD (EndoPAT) assessment 		х																	Х	
Meals 										Х										

CONFIDENTIAL

Adverse events	X				
Prior and concomitant meds.	X				
1 Symptom driven physical examination					

- 1. Symptom driven physical examination.
- 2. Clinical laboratory profile Day 3: pre-dose and Day 6: pre-dose.
- 3. Safety urine sampling Day 3 pre-dose and Day 6 pre-dose.
- 4. Systolic and diastolic blood pressure, pulse, respiratory rate at all time points indicated. Temperature will be measured on Day -1 only (other visits if indicated). For details regarding vital signs, see Section 11.3.4.
- 5. Vital signs and ECG Day 2 to Day 7: both in association with the morning dose and the evening dose, pre-dose and 1-hour post-dose.
- 6. Day 1: pre-dose at 12 hours. Day 2: pre-dose at 24 hours. Day 3 to Day 7: trough concentration (Ctrough) pre-morning dose samples, see Section 11.4.1.
- 7. PK urine sampling pre-dose and 0-12 hours post-dose.
- 8. Cohort B4 only. The EndoPAT assessment will be performed before the first IMP administration (Day -1 or Day 1) and 30±10 minutes after IMP administration on Day 7 (morning or evening dose). Subjects must fast for at least 4 hours prior to the EndoPAT assessment until end of assessment.
- 9. Standardised meals on Day -1, Day 1, Day 7 and Day 8, non-standardised meals on Day 2 to Day 6. Breakfast at least 1 hour post dose, lunch, snack, dinner and optional evening snack at approximately 4, 7 and 9 and 10 h post-dose. Optional evening snack at least 2 hours before or 1 hour after IMP administration.

#### Table 8.1-5 Detailed schedule of events Part B (MAD) Day 8 to Day 10

Day		-			-	-	D	ay 8							Day 9	Day 10
Assessment/time-point (hh:mm)	Pre- dose	00:00	00:20	00:40	01:00	01:30	02:00	03:00	04:00	06:00	08:00	10:00	12:00	16:00	24 h post last dose	48 h post last dose
Clinical Laboratory profile	X															X
Safety urine sampling	X															X
Urinalysis (dipstick)	X															
Vital signs	X			X			X		Х	X		X			X	X
12-lead ECG	X			X			X		Х	X		X			X	X
IMP administration		Х														
Blood sampling for PK and metabolite profiling	X1		X	X	X	X	X	X	X	X	Х	X		X	Х	X
Urine sampling for PK and metabolite profiling 			X 													
Meals 		X														
Adverse events		X														

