# 9.6 Restrictions during the trial period

## 9.6.1 *General restrictions*

The subjects must be willing to comply to the below restrictions during the entire trial duration i.e., from screening to the end-of-trial visit (or longer if specified).

• Contraception Requirements: The male volunteers are expected to use condom to prevent pregnancy and drug exposure of a partners and refrain from donating sperm from the date of dosing until 3 months after last dosing of the IMP. Fertile female partners are expected to use highly effective contraceptive methods with a failure rate of

< 1% to prevent pregnancy from at least 4 weeks prior to dose to 3 months after last dose (for details regarding contraceptive methods, refer to inclusion criterion No 5).

• Meals and Dietary Restrictions: Standardised meals will be served on Day -1 and Day 1 in Part A (SAD) and on Day -1, Day 1, Day 7 and Day 8 in Part B (MAD). Nonstandardised meals will be served on the other days. Lunch will be served at least 4 hours post-dose. Snack, dinner, and optional evening snack will be served approximately 7-, 9- and 11-hours post-dose, respectively.

For details on IMP administration in fasted and fed state, refer to Section 10.5.1.

Standardised meals: A menu option decided by CTC. The meal selection is standardised in the sense that the nutritional content of the meals should be similar at each time point of each treatment day.

- Fasting: In Part A (SAD), the subjects should be fasting overnight (10 hours) before Day 1 and until 4 hours post-dose (except in the fed cohort). In Part B (MAD), subjects must fast from 2 hours prior to each IMP administration until 1-hour post-dose. Water is allowed *ad libitum* at the clinic except 1 hour before dose and 1 hour after dose. The IMP will be taken with water (approximately 240 mL, including the volume of the IMP). Subjects participating in Part B, cohort B4 must fast for at least 4 hours prior to the EndoPAT assessment until end of assessment.
- Sun protection: Protection from the sun is required from each C106 administration until 3 days post dose in Part A and from the first until 3 days after the last C106 administration in Part B. Study subjects are required to follow the recommendations given by Centres for Disease Control and Prevention (CDC, see [45]):
  - Stay in the shade, especially during sun peak hours of 10 AM to 4 PM.
  - Wear clothing that covers arms and legs.

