# 10.5.2 Treatment administration Part B

Subjects in Part B (MAD) will be administered oral doses of C106, or placebo as randomised for 8 consecutive days. The proposed doses are 40, 100, 180 and 240 mg BID for 8 days.

Subjects will be administered the IMP with approximately 240 mL of water (including the volume of the IMP) by clinical staff from Day 1 to 8, *i.e.*, at all dosing occasions.

The first IMP dose should be taken prior to breakfast and the second dose after 12 hours, on all treatment days. On Day 8, only the morning dose will be administered. Fasting is required 2 hours before and 1 hour after both the morning and evening dose.

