#### 11.5.4 Pharmacodynamic assessment (Part B, cohort B4)

[figure not shown]
The PD effect on endothelial function will be assessed by EndoPAT at visits and time points specified in the schedule of events for Part B of the trial (Table 8.1-3 and Table 8.1-4) according to the manufacturer's instructions. The EndoPAT assessments should be done at approximately the same time of the day on both occasions.

The EndoPAT assessment will be conducted in a quiet and relaxed atmosphere. Before initiating the assessment, the subject will be supine for at least 15 minutes. The subjects will be instructed to remain as still as possible during the assessment period. EndoPAT bio sensors will be placed on the subjects right and left index fingers. If this finger is unsuitable (e.g., finger is cut or injured), a different finger may be used as long as the same finger is used on both hands. The same finger should preferably be used at both assessments. A cuff will be placed on the nondominant upper arm for occlusion of the brachial artery.

Each recording will consist of a 5-minute baseline assessment, a 5-minute occlusion assessment, and 5-minute post-occlusion assessment. During the post-occlusion period, blood flow is restored causing an endothelium-dependent vasodilation.

The EndoPAT software, provided with the device, will calculate the RHI and AI scores using a computerised automated algorithm as outlined below. The results will be recorded in the eCRF.

• RHI score: post-to-pre occlusion pulse amplitude tonometry signal ratio in the occluded arm relative to the same ratio in the control arm, and corrected for baseline vascular tone. RHI is a measure of endothelial function.

• AI: calculated from pulse amplitude tonometry pulses at the baseline period. AI is a measurement of vascular stiffness and reflects the structural nature and basal tonus of the vessel.

[figure not shown]
The time points of the initiation and completion of the EndoPAT assessment, the arm occluded, the fingers assessed and any significant deviations from the instructions for use will be recorded in the eCRF.

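### The Day 7 EndoPAT in cohort B4 may follow the evening dose, but the Part B meal times put food inside its 4-hour fast, and the passages need reconciling

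*Combined protocol and SAP*

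**What the plan says.** The synopsis, Section 8.1.2, Table 8.1-3 footnote 10 and Table 8.1-4 footnote 8 all give the same timing: a baseline on Day -1 or Day 1 before the first dose, and one reading 30±10 min "after IMP administration on Day 7 (morning or evening" dose).

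The fast is mandatory. The footnotes state "Subjects must fast for at least 4 hours prior to the EndoPAT assessment until end of assessment", and Section 9.6.1 repeats it: "Subjects participating in Part B, cohort B4 must fast for at least 4 hours prior to the EndoPAT assessment until end of assessment".

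Section 10.5.2 fixes the dosing interval: "The first IMP dose should be taken prior to breakfast and the second dose after 12 hours, on all treatment days". Table 8.1-4 footnote 9 gives the meals: "lunch, snack, dinner and optional evening snack at approximately 4, 7 and 9 and 10 h post-dose". It adds that the evening snack may be taken 2 h or more before dosing, or 1 h or more after. It lists Day 7 among the standardised-meal days and makes no exception for B4. Section 9.6.1 puts dinner at about 9 h too, but the evening snack at about 11 h.

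Section 11.5.4 adds: "The EndoPAT assessments should be done at approximately the same time of the day on both occasions".

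**The concern.** A site that uses the evening option finds two instructions that do not fit together: the meal footnote places food in hours that the EndoPAT rule requires to be food-free. Different staff could resolve this differently.

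The option also lets some subjects be read in the morning before breakfast and others in the evening on a day with meals. The objective is the effect of C106 on endothelial function at steady state. It rests on one change in RHI and one in AI per subject, from 6 active and 2 placebo subjects. With 8 subjects there is little room to adjust for time of day or prandial state, so variation that the schedule could remove is better removed.

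**Working it through.** **Inputs.** Morning dose at 0 h. Evening dose at 12 h (Section 10.5.2). EndoPAT 20 to 40 min after the dose and fast of at least 4 h (Section 8.1.2). Dinner about 9 h and snack about 10 h (Table 8.1-4 footnote 9); snack about 11 h (Section 9.6.1). Recording lasts 5 + 5 + 5 = 15 min (Section 11.5.4).

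**Evening option.** Reading starts at 12:00 + 0:20 to 0:40 = 12:20 to 12:40 h. The fast must begin by 12:20 − 4:00 = 8:20 h to 12:40 − 4:00 = 8:40 h.

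| Food | Listed time | Gap to reading | Short of 4 h by |
|---|---|---|---|
| Dinner | 9:00 h | 3:20-3:40 h | 0:20-0:40 h |
| Snack, footnote 9 | 10:00 h | 2:20-2:40 h | 1:20-1:40 h |
| Snack, Section 9.6.1 | 11:00 h | 1:20-1:40 h | 2:20-2:40 h |

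Every gap is below 4 h across the whole ±10 min window. The 11 h snack also falls 1 h before the evening dose, inside the general 2-hour pre-dose fast of Part B.

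**Morning option.** Reading starts at 0:20 to 0:40 h and ends at 0:35 to 0:55 h. Breakfast is at least 1 h after the dose, so it comes later. The latest food that footnote 9 allows on the previous day is a snack 1 h after the evening dose, at 13:00 h. The gap is 24:20 − 13:00 = 11:20 h or more. The 4-hour fast is met with no change to the meals.

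**Baseline for an evening subject.** A Day 1 evening reading would follow the first dose, so the same-time rule moves this baseline to Day -1. Footnote 9 times meals from the dose, and Day -1 has no dose. The meal clock for that baseline is therefore undefined, although the 4-hour fast still applies.

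**PK alongside the reading.** Samples in Tables 8.1-4 and 8.1-5:
- Day 1: pre-dose + 10 post-dose + the 12 h sample = 12.
- Days 2 to 7: 6 pre-morning samples.
- Days 8 to 10: pre-dose + 10 up to 10 h + samples at 16, 24 and 48 h = 14.

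The total is 12 + 6 + 14 = 32, which matches Table 12.2-1. Seven of these samples (pre-morning, Days 2 to 8) fall 12 h after an evening dose, and none falls earlier than that after an evening dose. Day 7 has no post-dose sample after either dose. A morning reading can be set against the Day 8 morning profile, which has samples at 0:20 and 0:40 h. An evening reading has no such counterpart.

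**The case against.** The strongest reply is that nothing in the plan makes the reading postprandial. The fast is a firm requirement written for B4, while meal times are approximate and the evening snack is optional. A compliant site would serve dinner 20 to 40 min earlier and omit the snack before the dose. This stands: the defect is an unreconciled conflict, not a planned postprandial reading. It does not remove the conflict, because footnote 9 expressly allows a snack 2 h before dosing and says nothing about B4.

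Second, the endpoint is a within-subject change, and both the same-time rule and the fast cover both readings. That limits bias in each subject's change score. It does not make the 8 change scores alike in clock time or prandial state.

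Three stronger readings are tempting, and the documents do not support them:
- A reader might infer that evening doses are never PK-sampled. Seven 12 h trough samples exist; what is missing is the absorption phase and peak. The Day 7 morning dose has no post-dose sample either.
- A reader might infer that an evening reading is off-peak. The 20-40 min window equals the Tmax of 20-40 min reported from Part A (Sections 6.1.7 and 8.3.2). Those data follow a fast of at least 10 h, and no evening or fed Tmax is reported, so a shift is possible but not shown. The 2-hour dosing fast is no evidence for one, since the 4-hour rule governs this dose.
- A reader might infer from Table 8.1-4, where the Day 7 tick sits in the morning column, that the evening is excluded. Vital signs are ticked the same way although footnote 5 covers both doses, and footnote 8 states the option outright.

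**Conclusion.** The evening option, the 4-hour fast and the Part B meal times cannot all be followed as listed. Dinner is 20 to 40 min too late and the optional snack 1:20 to 2:40 h too late, depending on which section sets its time. This assumes that meals are served at the stated times, that the 12 h interval is kept, and that the 30±10 min window marks the start of the recording. Counting from the start of each meal is the lenient choice, since time spent eating shortens the gaps.

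The effect on RHI or AI cannot be derived from the documents, which give no variability or meal effect for either measure. What can be said is that mixed timing adds avoidable between-subject variation to a comparison of 6 with 2 subjects. Severity is minor: the endpoint is exploratory, confined to one cohort, and may be reported outside the clinical trial report.

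**What to change.** **Preferred.** In Section 8.1.2, the synopsis, Table 8.1-3 footnote 10 and Table 8.1-4 footnote 8, set the Day 7 EndoPAT at 30±10 min after the morning dose and the baseline on the morning of Day 1 before the first dose. Do both after the overnight fast and before breakfast. This satisfies the fast, the same-time rule and the meal schedule together, and lines the reading up with the Day 8 morning PK profile.

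**If the evening option is kept.** Amend Table 8.1-4 footnote 9 and Section 9.6.1 so that, for B4 evening readings, the last food is finished at least 4 h before the EndoPAT and no evening snack is served before the dose. Apply the same rule to the matching Day -1 baseline. The 10 h and 11 h snack times in the two places should be reconciled in the same edit.

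**Cost.** A wording change for one cohort, less scheduling freedom, and a fuller Day 1 pre-dose period. Subjects are dosed at most 3 at a time on separate days, and a session takes about 30 min (15 min supine plus 15 min recording), so staggered mornings look workable. The documents do not state device or staff numbers, so the site should confirm this.
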